# 8.0 Selection of study Population

The subject population will comprise male and female subjects of any race, aged between 50 and 80 years at Day 1, with a previous diagnosis of Parkinson's disease and a medical history of excessive daytime sleepiness confirmed with an Epworth Sleepiness Scale (ESS) > 12 at screening which correlates to at least moderate sleepiness ("moderate excessive" [13-15] and "severe excessive" [16-24]). Prior to any and all study-specific examinations, subjects will be informed as to the extent and nature of their study participation and will be given the opportunity to provide their written informed consent.

Approximately 48 active study sites globally will randomize a total of 230 subjects in order to have at least 200 completed subjects (50 completed subjects per treatment group, assuming an early withdrawal rate of around 15%). Recruitment will be competitive throughout all counties and sites.

Both inclusion and exclusion criteria will be assessed during the screening period and reconfirmed during the baseline period (see Section 8.1 and Section 8.2, respectively). Corresponding information should be provided in the eCRF.

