#### 11.0 Statistical Methods and Determination of Sample Size

#### 11.1. Statistical and analytical plans

The statistical analysis will be performed by the Department of Biostatistics of Linical, using SAS® version 9.2 or later.

Statistical significance will be assessed for two-sided probability values < 0.05.

All descriptive variables will be tabulated. Quantitative variables will be described showing their number of available and missing observations, mean, median, standard deviation (SD), the range (minimum and maximum) and the first and third quartiles. Frequency and percentage will describe qualitative variables. Missing values will be tabulated with their frequency but will not be included in the calculation of percentages.

The main population for the efficacy analysis will be the intent to treat population (ITT). The per protocol population (PP) will be analysed also as a sensitivity analysis.

The main population for the safety analysis will be the safety population (SAF), defined as all the subjects who have received at least one dose of study treatment.

Full details of the statistical analysis will be given in a Statistical Analysis Plan (SAP) which will be prepared, approved and signed before the database closure, and so before the subjects' evaluability assessment.

Any deviation from the original SAP will be included and reported in the clinical study report (CSR).

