4 DESIGN OF THE STUDY

This phase 2b study is designed as multicentre, multinational, randomized, double blind, parallel group and placebo controlled with three doses of Bavisant (0.5, 1, and 3 mg/d) in subjects with excessive daytime sleepiness with Parkinson's disease. This study will involve approximately 230

subjects from around 48 sites globally. Eligible subjects will be randomly allocated at a ratio of 1:1:1:1 to either Bavisant (at doses of 0.5, 1 and 3 mg/d) or placebo. After signing the study informed consent, subjects meeting the UK PDS Brain Bank Clinical Diagnostic Criteria for Parkinson's disease (see details in the protocol Appendix 18.2) will enter a screening period (lasting up to 3 weeks) followed by a baseline period (lasting up to 1 week). Key inclusion / exclusion criteria will be verified to determine subject eligibility at the screening, baseline periods and prior to randomisation, including the suicide risk assessment following the FDA Guidance for Industry on Suicidal Ideation and Behavior. There is a 6 weeks treatment period, starting on Day 1, followed by a safety follow-up at least 4 weeks after completion of the treatment period. Additional unscheduled visits may be required based on the investigators' judgement at the end of study visit or at the safety follow-up. For early termination, all the assessments of the treatment week 6 visit should be performed, if possible, including the safety follow-up 4 weeks after the last investigational medicinal product (IMP) administration. The figure below describes the study flow graphically.

Figure 1

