5 SAMPLE SIZE AND POWER ESTIMATION

A total of 200 completed subjects will be evaluated for the study (50 completed subjects per treatment group, with expected early withdrawal rate of around 15%).

The assumptions used for the sample size calculation are a mean absolute change in the Epworth Sleepiness Scale (ESS) from baseline to the end of the 6-week treatment period of at least 3.0 points (minimum change considered as clinically relevant) and a standard deviation of 5.0 (based on a comparable study of Modafinil in a similar population recruited at one centre (3) which showed a standard deviation in the ESS between 3.5 at baseline and 4.8 at the end of the treatment period) and a reduction in ESS of 2.7 points for subjects treated with Modafinil.

The confirmation of the hypothesis of detecting a mean difference in ESS of 3.0 points vs. baseline requires a sample size of 25 subjects per group (intragroup $\Delta=3.0$; $SD=5.0$; two-side $\alpha=0.05$; $\beta=0.20$; power=80%; one-sample t-test).

The additional endpoint of showing a statistically significant difference of at least 3.0 points in ESS between Bavisant and placebo requires a sample size of 50 subjects per group (between treatment $\Delta=3.0$; $SD=5.0$; two-side $\alpha=0.05$; $\beta=0.20$; power=80%; two-sample equal-variance t-test).

The effect size of Bavisant in EDS is unknown and smaller changes in ESS may be clinically useful according to its profile, and higher variability is expected in this multicentre study; so the sample size of 200 completed subjects (50 per treatment group) is proposed in order to cover both the confirmation of an intragroup change of at least 3.0 points vs. baseline, and the between-group difference of at least 3.0 points change vs. placebo.

The Maintenance of Wakefulness Test (MWT) will be performed in a minimum of 20 subjects per group (80 overall) in order to be enough to show statistically significant differences if the expected MWT absolute change from baseline differs at least in one standard deviation (effect size = 1.0).

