6 ANALYSIS SETS

The safety population (SAF) will be defined as all subjects who have received at least one dose of the study treatment.

Sponsor BenevolentAI Bio

Project Code ... BB-2001-201b

The intent to treat population (ITT) will be defined as all randomized subjects who have taken at least one dose of study treatment.

The per protocol population (PP) will be defined as all subjects in the FAS who do not experience a major protocol deviation.

Protocol deviations will be defined as deviations from the procedure outlined in the protocol. Protocol deviations will be identified for each patient in the Data (blind) Review & Evaluability Determination meeting will be held prior to the treatment unblinding. They will be assessed as “minor” or “major” according to the possible impact expected on efficacy results. Minor and major protocol deviations will be fully documented in the Protocol Deviation Document prior to unblinding. Specific data sets will be produced and transferred to Biostatistics department in order to allow the appropriate definition for the Per Protocol Population.

Since the reasons for excluding patients from the analysis cannot be entirely foreseen at the time of writing the statistical analysis plan evolving trial conduct may require some further definition of patients to be excluded, at the end of the trial, but prior to unblinding.

Aspects to be considered (but not limited to) when determining the evaluability of data are as follows:

- Inclusion and exclusion criteria
- Acceptable timings for visit dates and measurements
- Compliance with treatment
- Incorrect randomization/treatment
- Concomitant therapies

As far as possible ITT principle will be guaranteed so it is not expected to have protocol deviations excluding patients from the ITT population.

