7 PRESENTATION OF DATA

Tables and listings will be produced in accordance with the principles outlined by the ICH E3 guideline.

Categorical data will be summarized with absolute and relative frequencies (percentage), missing data will not be considered in the percentage calculation, and numerical data will be summarized with the number, mean, median, standard deviation (SD), the range (minimum and maximum), and the first, third quartiles and 95% confidence interval (if applicable). Throughout the presentation of the study results the four treatment groups will be displayed separately. For safety a new column summarizing data for the three active treatment arms together will be added.

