12 STATISTICAL METHODOLOGY FOR SAFETY ENDPOINTS

The baseline value is defined as the last available value before the first dose of double-blind IMP taken.

The analysis of the safety variables will be essentially descriptive and no systematic testing is planned.

The observation period of safety data will be divided into 2 sub-periods:

- The pre-treatment period is defined as the time between the date of signed informed consent and the first dose of double-blind IMP.
- The on-Treatment period (TEAE period): is defined as the Date/ time from first dose of double-blind IMP.

12.1 Incidence of Adverse Events (AEs), Serious Adverse Events (SAEs), and Adverse Events of Special Interest (AESIs) such as headache, nausea and insomnia

All adverse events will be analysed and determined to be either pre-treatment or treatment-emergent. If an adverse event date/time of onset (occurrence, worsening, or becoming serious) is incomplete, an imputation algorithm will be used to classify the adverse event as pre-treatment or treatment-

emergent. The algorithm for imputing date/time of onset will be conservative and will classify an adverse event as treatment emergent unless there is definitive information to determine it is pre-treatment.

All adverse events (including serious adverse events and adverse events of special interest) will be coded to a lower-level term (LLT), preferred term (PT), high-level term (HLT), high-level group term (HLGT), and associated primary system organ class (SOC) using the version of Medical Dictionary for Regulatory Activities (MedDRA) version 20.1. Lower-level term (LLT) will not be presented in the analysis. Number of patients in the SAF will be used as denominator for the percentages calculation.

12.2 Incidence of suicidal ideation (C-SSRS) findings from screening/baseline to the end of the 2-week and the 6-week treatment period and safety follow-up

Patients with a positive response on the C-SSRS (an answer of ‘yes’ to any of the 6 questions) will be described through absolute frequency and percentage at visit 2 (day 14) , visit 3 (day 42) and globally (at any time in the follow-up period) in the study. This percentage will be calculated using the number of patients with C-SSRS evaluation done at the corresponding visit as denominator.

12.3 Incidence of positive psychotic symptoms (BPRS+) findings from screening/baseline to the end of the 2-week and the 6-week treatment period and safety follow-up

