12.4 Incidence of physical examination, vital signs

Physical examinations will consist of the following body systems: (1) general, appearance; (2) extremities; (3) skin; (4) head and neck; (5) eyes, ears, nose and throat; (6) lungs and chest; (7) heart/ cardiovascular; (8) neurological; (9) abdomen / gastrointestinal; (10) liver; (11) musculoskeletal; and (12) other. Each system should be assessed as normal or abnormal and in the last case if that is clinically relevant or not. The incidence of patients with at least one change from normal at baseline to abnormal at Visit 3 will be calculated for each of the body systems.

Potentially Clinically Significant Abnormality (PCSA) are detailed below for Vital signs:

- WEIGHT change from baseline >5%
- Number of breaths per minute <12 or >25. Percentages of patients with a normal respiratory rate (RR) at baseline and an abnormally high or low RR at Visit 3 will be summarized by treatment.

Incidences will be calculated using the number of patients in the safety population as denominator.

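### SAP 12.4 to 12.7 count treated subjects who were never assessed as having no safety finding, against the plan's own rule that missing data stay out of percentages

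*SAP*

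**What the plan says.** SAP 12.4 (physical examination, vital signs) states: "Incidences will be calculated using the number of patients in the safety population as denominator". The same sentence closes 12.5 (laboratory), 12.6 (blood pressure, heart rate, ECG) and 12.7 (eye examination). SAP 6 defines the safety population as "all subjects who have received at least one dose of the study treatment"; no post-baseline assessment is needed to belong to it.

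Three other places set a different rule:

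- SAP 7, for categorical data in general: "missing data will not be considered in the percentage calculation".
- Protocol 11.1: "Missing values will be tabulated with their frequency but will not be included in the calculation of percentages".
- SAP 12.2, for the C-SSRS: "This percentage will be calculated using the number of patients with C-SSRS evaluation done at the corresponding visit as denominator".

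SAP 14 declares that the statistical content of the protocol is unchanged.

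The schedule matters here. Protocol 8.4.1.6, 8.4.1.10, 8.4.1.12, 8.4.1.13 and Appendix 18.15 give physical examination, laboratory tests, ECG and eye examination one scheduled post-baseline time point: Visit 3 or early termination, or after treatment for the eyes. Vital signs, blood pressure and heart rate are also taken at Visit 2 and follow-up (Protocol 8.4.1.7). Protocol 7.1 asks for the week 6 assessments at early termination where possible. SAP 4.1 lets an early termination visit stand in for Visit 3 only on days 22 to 45.

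**The concern.** A percentage that divides by everyone treated, when some were never examined, treats an absent measurement as a normal one. The result can equal the rate among examined subjects but never exceed it, so any error relative to that rate runs towards fewer findings. Safety is summarised without testing, so readers will compare these percentages across placebo and three doses by eye.

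There is also a plain programming problem. One programmer could follow SAP 7 and another SAP 12.4 to 12.7, and their tables would differ.

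A second dilution affects rates defined as a move from normal to abnormal, as in SAP 12.4 for body systems and respiratory rate. A subject already abnormal at baseline cannot have the event, yet stays in the denominator.

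**Working it through.** **Inputs.** SAP 5 plans "50 completed subjects per treatment group, with expected early withdrawal rate of around 15" per cent. Protocol 8.0: "Approximately 48 active study sites globally will randomize a total of 230 subjects". SAP 4: "Eligible subjects will be randomly allocated at a ratio of 1:1:1:1". The documents state no safety incidence and no withdrawal rate by arm, so the 20% evaluated rate and all unassessed shares by arm below are assumptions.

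**The plan's own figure.** 200 completers × 1.15 = 230, the stated total. Dividing instead gives 200 / 0.85 = 235.3, so 236. As planned, 30 / 230 = 13.0% would be non-completers. Nothing below depends on this difference. One arm is 230 / 4 = 57.5, taken as 58.

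**Formula.** Let k be subjects with a finding, N treated, u unassessed and m = u / N. The SAP rate is k / N and the evaluated rate is k / (N − u). Therefore SAP rate = evaluated rate × (1 − m).

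**One arm of 58 with 10 findings.** The SAP rate is 10 / 58 = 17.2% whatever the number unassessed.

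| Unassessed | Evaluated rate |
|---|---|
| 3 (about 5%) | 10 / 55 = 18.2% |
| 9 (about 15%) | 10 / 49 = 20.4% |
| 14 (about 25%) | 10 / 44 = 22.7% |

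**Allowing for early termination visits.** Let c be the share of withdrawn subjects who supply a usable assessment. With 15% withdrawal, m = 0.15 × (1 − c), and an evaluated rate of 20% is shown as:

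- c = 0: 0.20 × 0.85 = 17.0%
- c = 0.5: 0.20 × 0.925 = 18.5%
- c = 0.8: 0.20 × 0.97 = 19.4%
- c = 1: 20.0%

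**Unequal arms (assumed).** With the same 20% evaluated rate in both arms, 5% against 25% unassessed gives 19% against 15%, a ratio of 0.75 / 0.95 = 0.79. A real ratio of 0.95 / 0.75 = 1.27 would then look like 1.0. With 10% against 20% unassessed the rates are 18% and 16%, a ratio of 0.89.

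**Already abnormal at baseline (assumed).** If 10% are abnormal at baseline, a 20% rate among those at risk is shown as 0.20 × 0.90 = 18.0%, and as 18.0% × 0.85 = 15.3% with 15% unassessed as well. If 30% are abnormal, the figures are 14.0% and 11.9%.

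**What the evaluated rate assumes.** Take 20% among assessed subjects and 15% unassessed. The rate in all treated subjects is 0.85 × 20% + 0.15 × p, where p is the rate the unassessed would have had. It is 17% if p = 0, 20% if p = 20% and 23% if p = 40%.

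**Visit windows.** SAP 12.4 ties physical examination and respiratory rate to Visit 3. On a strict reading of SAP 4.1, a subject who stops before day 22 and is examined at early termination has no Visit 3 slot. That subject remains in the denominator but cannot reach the numerator.

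**The case against.** The strongest reply is that the specific sentences in SAP 12 override the general rule in SAP 7, and that dividing by all treated subjects is a recognised convention. As a choice it could be defended, but it is not declared as one: Protocol 11.1 says the opposite, SAP 14 reports no change, and SAP 12.2 uses the other convention in the same chapter.

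A reader might infer that every one of these rates is understated, and most so in the arm with most drop-outs. The documents do not support that:

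- Blood pressure and heart rate are measured at several visits and SAP 12.6 names no visit. If any post-baseline reading counts, few treated subjects would be unassessed and the effect should be small.
- A withdrawn subject is not necessarily unassessed. Protocol 8.4.2 and 8.5.2 call for the week 6 procedures at early termination, so 17% in place of 20% is the worst case at 15% withdrawal.
- No withdrawal rate by arm is given, and what counts is the share unassessed, not the share withdrawn. The background on dose-related events makes an imbalance possible; it does not establish one. Protocol 7.2 says the listed events were less frequent at 1 and 3 mg than at 10 mg.
- The shortfall is relative to the evaluated rate. If unassessed subjects would have had no findings, the safety-population figure is the correct one.

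The consequences are also limited. Nothing is tested and counts are unaffected. Clinically significant laboratory and ECG changes are also recorded as adverse events, the laboratory shift tables show the baseline category, and eye findings are listed in full. These points narrow the concern, but the contradiction and the arithmetic stand.

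**Conclusion.** The SAP is inconsistent as written and should be corrected. The denominators in 12.4 to 12.7 conflict with SAP 7, Protocol 11.1 and SAP 12.2, and they understate each rate, relative to the evaluated rate, by exactly the unassessed share. For findings with a single scheduled post-baseline time point, a 20% evaluated rate would be shown between 17.0% and 20.0% at the planned withdrawal, depending on how many withdrawn subjects are assessed. Normal-to-abnormal rates fall further with the share already abnormal at baseline. A distorted comparison between doses is a possibility that depends on unequal missing assessments, not something the documents show. Calling the shortfall a bias assumes that unassessed subjects resemble assessed ones, which the plan can neither confirm nor rule out. Reporting the number unassessed lets readers judge.

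**What to change.** Reword SAP 12.4 to 12.7 as follows:

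- Use as denominator the subjects with at least one post-baseline assessment of the parameter.
- Require a baseline value only for change-from-baseline criteria, and a normal baseline for normal-to-abnormal shifts. Purely absolute limits, such as QT above 500, need none.
- Where a criterion combines absolute and change limits, as for blood pressure and heart rate, keep assessed subjects who lack a baseline and judge them on the absolute limit, so that no real event is dropped.
- Name the visits that count and use the same ones in numerator and denominator. State that an early termination assessment counts as the end-of-treatment value whatever the study day; otherwise subjects stopping before day 22 would still dilute the rates tied to Visit 3.
- Show n/N evaluated and the number not assessed in each arm, with a note that the evaluated rate assumes unassessed subjects resemble assessed ones.
- Keep the safety population as denominator for adverse events.

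The cost is SAP wording and the matching table shells. No extra data, visits or subjects are needed.

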12.5 Incidence of laboratory tests findings (haematology and biochemistry)

Clinical laboratory values after conversion will be analysed into standard international units and international units will be used in all listings and tables. Shift tables will be produced presenting the intra-patient change between below normal, normal and above normal for each of the laboratory parameters, according to the appropriate laboratory ranges.

Incidences will be calculated using the number of patients in the safety population as denominator.

12.6 Incidence of cardiovascular safety findings (blood pressure, heart rate, ECG QT/QTc)

Incidence of Potentially Clinically Significant Abnormality (PCSA) as detailed below will be described for blood pressure and ECG:

- Blood Pressure
 - SBP: ≤ 95 mmHg or decrease from baseline ≥ 20 mmHg or ≥ 160 mmHg or increase from baseline ≥ 20 mmHg
 - DBP: ≤ 45 mmHg or decrease from baseline ≥ 10 mmHg or ≥ 110 mmHg or increase from baseline ≥ 10 mmHg
- Heart rate
 - < 50 bpm or decrease from baseline ≥ 20 bpm or ≥ 100 or increase ≥ 20 bpm from baseline.
- ECG
 - QTc (> 450 for males and > 470 for females) for both Bazett and Friedericia.
 - QT > 500

Incidences will be calculated using the number of patients in the safety population as denominator.

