### 7.0 Investigational Plan

# 7.1. Overall Study Design and Plan: Description

This phase 2b study is designed as multicentre, multinational, randomized, double blind, parallel group and placebo controlled with three doses of Bavisant (0.5, 1, and 3 mg/d) in subjects with excessive daytime sleepiness with Parkinson's disease. This study will involve approximately 230 subjects from around 48 sites globally.

Eligible subjects will be randomly allocated at a ratio of 1:1:1:1 to either Bavisant (at doses of 0.5, 1, and 3 mg/d) or placebo.

After signing the study informed consent, subjects meeting the UK PDS Brain Banks Diagnostic Criteria for Parkinson's disease (see details in Appendix 18.2) will enter a screening period (lasting up to 3 weeks) followed by a baseline period (lasting up to 1 week). Key inclusion / exclusion criteria will be verified to determine subject eligibility at the screening, baseline periods and prior to randomisation, including the suicide risk assessment following the FDA Guidance for Industry on Suicidal Ideation and Behavior.

[figure not shown]
There is a 6 weeks treatment period, starting on Day 1, followed by a safety follow-up at least 4 weeks after completion of the treatment period. Additional unscheduled visits may be required based on the investigators' judgement at the end of study visit or at the safety follow-up. For early termination, all the assessments of the treatment week 6 visit should be performed, if possible, including the safety follow-up 4 weeks after the last IMP administration.

A schematic of the study design is included in Figure 1 and the schedule of assessments is listed in Appendix 18.15.

Protocol No.: BB-2001-201b 07/Nov/2018 EudraCT No.: 2017-000877-35 Page 39 / 142

Figure 1. Study figure

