### 11.1.7 Safety Analyses

Adverse events, adverse events of special interest, serious adverse events, serious and related adverse events will be coded using the latest available MedDRA version and their corresponding incidences will be summarised as overall events, related events, and events by intensity. AEs will be summarised by MedDRA preferred term and system organ class (primary SOC). Summaries of AEs by preferred term and decreasing frequency and by maximum severity will also be prepared.

Physical examination changes, vital signs changes, laboratory tests changes, cardiovascular changes, ocular changes, suicidal ideation (C-SSRS) findings, and positive psychotic symptoms (BPRS+) findings will be described for the different treatment groups and assessed as either clinically or non-clinically significant findings.

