The BPRS consists of 4 symptom constructs ((#4, #11, #12, and #15) which ranges from 1 (not present) to 7 (extremely severe). 0 is entered if the item is not assessed. The total score is calculated as the sum of the scores of the 4 items. Incidence of patients with an increase and incidence of patients with a decrease from baseline in the BPRS+ total score will be described at the corresponding visit. Also the change from baseline will be descriptively analysed as a numerical data (see section 7 for further reference) for all patients, for patients with BPRS+ total score reduction and for patients with BPRS+ total score increase.

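### SAP 12.4–12.6 name only threshold counts and normal-range shift tables for QTc, blood pressure, heart rate, weight, respiratory rate and laboratory values, and no numerical change from baseline

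*SAP*

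**What the plan says.** SAP 12.6 opens with "Incidence of Potentially Clinically Significant Abnormality (PCSA) as detailed below will be described for blood pressure and ECG" and then lists limits. SBP, DBP and heart rate are flagged by an absolute value or by a change from baseline, with rises and falls in the same line. QTc (both corrections) is flagged above 450 for males and 470 for females, and QT above 500. Neither QTc nor QT has a change criterion.

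SAP 12.5 plans for laboratory values: "Shift tables will be produced presenting the intra-patient change between below normal, normal and above normal for each of the laboratory parameters". SAP 12.4 gives weight one criterion, "WEIGHT change from baseline >5" per cent, and respiratory rate a low and a high limit.

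For BPRS+, SAP 12.3 goes further: "Also the change from baseline will be descriptively analysed as a numerical data", with a pointer to SAP 7.

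Protocol 11.1.7 lists "Physical examination changes, vital signs changes, laboratory tests changes, cardiovascular changes, ocular changes", among others, as things to be described by treatment group and assessed for clinical significance. SAP 12 adds: "The analysis of the safety variables will be essentially descriptive and no systematic testing is planned".

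**The concern.** Protocol 8.4.1.7, 8.4.1.10 and 8.4.1.12 collect these variables as measurements before and after treatment. A moderate drug effect on such a variable usually appears as a shift of the whole distribution. A count above a limit registers only the subjects whom the shift carries across that limit.

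This matters most for QTc. Exclusion criterion 11 removes subjects above the same 450/470 limits that the SAP later uses as its safety flag. A general rise therefore becomes visible only through subjects who entered close to the limit. For blood pressure and heart rate, a one-directional shift adds to one tail and takes from the other, and the combined flag hides part of it.

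The trial compares three doses and names cardiovascular safety as an endpoint. A dose-related mean rise in QTc, heart rate or blood pressure would bear on the choice of dose. The tables named in 12.4–12.6 could miss it and be read as showing no effect.

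**Working it through.** **Step 1: does another section supply the missing table?**

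- SAP 7 and Protocol 11.1 fix the statistics for numerical data (mean, median, SD, range, quartiles, and in SAP 7 a 95% CI if applicable). They set the format but do not say which safety variables get a change-from-baseline table.
- SAP 13.1 says baseline safety parameters come with summary statistics. That concerns baseline values, not change.
- SAP 12.3 shows how the SAP asks for numerical change when it wants it. SAP 12.4–12.6 contain no such sentence.
- SAP 17 leaves table shells to a separate document.

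The gap remains: a programmer following 12.4–12.6 literally produces no mean change.

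**Step 2: inputs for the size of the loss**

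The plan has no power or precision figure for any safety variable, so there is none to reproduce. From the documents come 50 completed subjects per group (Protocol 11.2); about 57 randomised per arm, since "This study will involve approximately 230 subjects from around 48 sites globally" and 230/4 = 57.5; and the general rule "Statistical significance will be assessed for two-sided probability values < 0.05". Every mean, SD and shift below is an assumption. Power here measures information only.

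**Step 3: QTc, +10 ms**

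Model: male limit 450, baseline SD 18 truncated at 450, SD of change 15, 57 per arm.

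| Baseline mean | Rate >450, no shift | Rate >450, +10 ms | Subjects of 57 | Fisher power | Chi-square power |
|---|---|---|---|---|---|
| 390 | 0.5% | 1.6% | 0.3 vs 0.9 | 0% | 8% |
| 400 | 1.5% | 4.1% | 0.9 vs 2.3 | 1% | 14% |
| 410 | 3.6% | 9.0% | 2.1 vs 5.1 | 10% | 22% |
| 420 | 7.1% | 16.3% | 4.0 vs 9.3 | 23% | 33% |

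For the mean change, the noncentrality is 10/(15 × √(2/57)) = 3.56, which gives 94% power. With 50 per arm it is 10/(15 × 0.2) = 3.33, which gives 91%.

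Over baseline means 390–420 and SD of change 12–20, with 50 per arm, the threshold comparison (Fisher) has about 0–21% power and the mean-change comparison 68–99%.

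**Step 4: SBP, +8 mmHg**

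The change criterion alone, with SD of change 12:

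- No shift: 2 × P(Z > 20/12 = 1.67) = 9.6%.
- With shift: P(Z > 12/12 = 1.00) + P(Z < −28/12 = −2.33) = 15.87% + 0.98% = 16.85%, about 17%.

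With 57 per arm, Fisher power is 13%, against 94% for mean change. Adding the absolute limits (baseline assumed N(132, 16)), with 50 per arm and SD of change 12–15, gives about 8–20% against 73–94%.

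**Step 5: heart rate, +5 bpm**

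The change criterion alone, with SD of change 8:

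- No shift: 2 × P(Z > 20/8 = 2.50) = 1.2%.
- With shift: P(Z > 1.875) + P(Z < −3.125) = 3.04% + 0.09% = 3.1%.

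With the absolute limits (baseline assumed N(72, 10)), 50 per arm and SD of change 8–10, the figures are about 1–3% against 68–91%.

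In steps 4 and 5 the spread covers both the SD of change and whether change is correlated with baseline; a correlation makes baseline adjustment more efficient.

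**Step 6: what the added interval would show**

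The unadjusted 95% half-width for a difference in mean change, with 50 per arm, is 1.984 × SD × √(2/50) = 1.984 × SD × 0.2:

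- QTc, SD 15: 5.95 ms.
- Heart rate, SD 8–10: 3.17–3.97 bpm.
- SBP, SD 12–15: 4.76–5.95 mmHg.

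No calculation was made for weight or laboratory values.

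**The case against.** The strongest reply is that the SAP does not rule numerical summaries out. SAP 7 and Protocol 11.1 set general rules for quantitative data, SAP 1 says the SAP does not change the protocol analysis, and table shells are separate. The protocol also defines these endpoints as incidences of findings and wants the changes classed by clinical significance, which points to categories. This stands in part. A reader might infer that the SAP commits to reporting categories only, and the documents do not support that. What they support is that 12.4–12.6 name only categories and leave numerical change unassigned.

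The power comparison is also open to attack. No safety test is planned, so the chance of seeing a shift is undefined within the plan. Fisher's test is conservative for rare events; chi-square gives 8–33% in the QTc table above. Only the male limit was modelled. These points bar any single figure. They do not reverse the direction, since mean change carries much more information in every scenario run.

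Blood pressure, heart rate and weight do have change criteria, and part of the loss comes from combining directions. For SBP in step 4, counting rises alone at 57 per arm would raise Fisher power from 13% to 37%. The SAP plans the combined flag, though, and 37% is still far below 94%.

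Last, differences from placebo with intervals go beyond closing the textual gap. They remain compatible with a descriptive safety analysis if given without p-values.

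**Conclusion.** The point holds as a gap in specification. For QTc, blood pressure, heart rate, weight, respiratory rate and laboratory values, the SAP names threshold incidences and shift tables and no numerical change from baseline, and the general display rules do not fill that gap. It is most serious for QTc.

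The size depends on assumed distributions: at 50 per arm, roughly 0–21% against 68–99% for QTc +10 ms, 8–20% against 73–94% for SBP +8 mmHg, and 1–3% against 68–91% for heart rate +5 bpm. A reader might infer one headline pair, such as 6% against 95%, covering all these variables. The documents do not support that. They give no safety means, SDs, shifts or tests; the criteria differ between variables; and that pair is one QTc scenario (baseline mean 415, SD of change 15). No size is claimed for weight or laboratory values.

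This is a cheap improvement, not a flaw that undermines the safety analysis.

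**What to change.** Add to SAP 12.4–12.6:

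- For QTcF, QTcB, heart rate, SBP, DBP, weight and each laboratory parameter: numerical change from baseline by arm and by each visit at which the variable is measured, with the SAP 7 statistics.
- For QTcF, heart rate, SBP and DBP: the difference from placebo in mean change for each dose with its 95% CI, labelled descriptive and unadjusted for multiplicity, without p-values.

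Keep the PCSA counts and shift tables, which serve to find individual outliers.

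The cost is a few sentences and some standard tables from data already collected, with no new procedures. The downside is a longer safety output with several unadjusted intervals, which must be labelled so that they are not read as tests.
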